Visit 3, 4 and 5: 5 HV who completed visits 1 and 2 will be recruited to undergo development of TMS stimulation protocol at Duke BSRC. TMS Stimulation will be provided up to 20 minutes (at 10Hz) with a writing sample during stimulation. Subjects will also perform a writing assessment before and after each stimulation block. An fMRI will be performed after completion of each TMS stimulation session.

20 focal hand dystonia subjects who completed visits 1 and 2 will also be recruited to undergo 3 visits of TMS stimulation at Duke Brain Stimulation Center. The 3 visits will each be 1 week apart. 2 visits will involve active TMS and 1 visit will be sham TMS. During one of the active TMS visits, TMS coil will be applied to the premotor cortex for brain stimulation while during the other active TMS visit, TMS coil will be applied to the primary sensory cortex. TMS stimulation protocol will consist of 10Hz stimulation for up to 20 minutes with a writing task during the stimulation block. Subjects will undergo a writing assessment before and after each stimulation block and complete TMS side effects survey. Writing task is different from writing assessment in that writing task will only be used as part of the investigational therapy while writing assessment will be data collected for outcomes measures. fMRI will be performed after completion of each of the 3 TMS visits.

Background & Significance

- Should support the scientific aims of the research

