Furthermore, a meta-analysis of 5 TMS studies in WC dystonia subjects also demonstrated consistent albeit short-term benefit when TMS was applied at premotor cortex supporting its role in engaging dystonia brain circuitry(38–43) and supporting the idea that these regions are also linked by a common connection. A second potential cortical target is primary sensory cortex. Previous connectivity analysis in WC subjects demonstrated decreased functional connectivity between putamen and primary sensory cortex(27). Among the previous studies applying TMS to WC subjects, the study that showed the longest benefit (2weeks) targeted the primary sensory cortex(44). In this study, TMS stimulation will be applied to the premotor cortex during one visit and to primary sensory cortex during another visit to evaluate the optimal cortical target for modulating putamen activity using TMS in WC subjects.

Design & Procedures

- Describe the study, providing details regarding the study intervention (drug, device, physical procedures, manipulation of the subject or the subject’s environment, etc.). Discuss justifications for placebo control, discontinuation or delay of standard therapies, and washout periods if applicable. Identify procedures, tests and interventions performed exclusively for research purposes or more frequently than standard of care. Include alternative therapies, concurrent therapies discontinued per protocol, risk benefit ratio, and use of tissue/specimens. Discuss monitoring during washout periods if applicable. Include brief description of follow-up, if any.

Consent process and data collection will occur in a private room at the Duke Morreene Road Clinic or Duke brain Imaging Center or Duke Brain Stimulation Center in Red Zone of Duke South. All subjects

will sign an electronic single consent form uploaded to redcap or a printed hard copy. Any subject who wishes to sign their consent forms virtually, a blank consent form will be shared with subjects by redcap or emailed to them prior to the virtual visit. A phone or video visit will then be scheduled. At the virtual visit, an IRB approved study script will be used to review the research study with them for consenting purposes. The subject can then sign the consent form on redcap electronically or mail the signed hard copy to the study staff. The signed consent form will then be scanned and uploaded to Oncore and maestro care. Subjects can opt in or out of visits 2, and 3-5 of the research study.

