Visit 2: 70 FHD subjects and 70 HV from visit 1 will be recruited to undergo a functional MRI brain at Duke BIAC. To assess patient's baseline, subjects will copy a sentence using their dystonic **left or right hand** in fMRI suite alternated by periods of rest using an MRI compatible digital tablet. Writing task and control motor task will be back-projected onto a screen located at the head of the MRI bed using an LCD projector. Subjects will view the screen via a mirror system located in the head coil. Task onset will be electronically synchronized with the MRI acquisition computer using Cigal computer software. Task administration and collection of writing data will be computer controlled. The scanning session will take about 1.5 hr and include structural MRI, DTI, Swan, resting state fMRI and task-based fMRI.

BOLD images will be acquired using a GE Premier Performance 3T MRI scanner, which is an improved version of GE's FDA-approved Premier system, but with better capabilities for high-resolution imaging. All operational parameters on this improved system will be within FDA guidelines to meet the same minimal risk device criteria and ensure safety of human subjects. As such, an Investigational Device Exemption (IDE) is not necessary. The research conducted under this protocol is not to evaluate the safety and efficacy of this device.

A urine drug screen and pregnancy test prior to visits 3-5.

Visits 3, 4 and 5: 5 healthy volunteers who completed visits 1 and 2 will be recruited to undergo development of TMS stimulation protocol at Duke BSRC. Following protocol development, 20 focal hand dystonia subjects who completed visits 1 and 2 will also be recruited to undergo TMS stimulation at Duke BSRC. All 25 subjects will undergo the procedure as detailed below:

[figure not shown]

Figure 3: Sequence of events for research visits 3, 4, and 5. A) Overview of TMS stimulation, writing assessment and fMRI imaging. B) TMS session will be divided into 4 blocks of writing, each 5 minutes.

1. MRI Brain images from visit 2 will be uploaded to a neuro-navigation system (Brainsight: Rogue Research, Montreal, Canada) at the Brain Stimulation Service Stimulation Service Center

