 3. Healthy volunteers will undergo TMS stimulation protocol development. Subjects will receive 10Hz active stimulation at premotor cortex during one visit and primary sensory cortex during another visit for up to 20 minutes with stimulation intensity up to 120% of resting motor threshold which is within the published safety guidelines (47) and based on previously published protocol used in multiple human studies(13–16). The resting motor threshold is a baseline stimulation intensity determined using the protocol in step 2. Additional stimulation parameters including duration of continuous stimulation, interstimulus interval, stimulation intensity, orientation of magnetic coil, biphasic or monophasic stimulation will be developed with healthy volunteers based on the published safety guidelines(47), writing assessment (includes writing and non-writing sampling) and feasibility within 20 minutes stimulation paradigm.
 4. WC subjects will undergo TMS stimulation visits 3, 4 and 5. 2 visits will include active TMS stimulation while the remaining one visit will be a control sham stimulation. Of the 2 active TMS stimulation visits, subjects will receive TMS at premotor cortex during one visit and at primary sensory cortex during the other active TMS visit. The dosage of active stimulation will be 10Hz for up to 20 minutes with resting motor threshold up to 120% which is within the published safety guidelines (47) and based on previously published protocol used in multiple human studies(13–16). During both active and sham stimulation blocks, subjects will be asked to perform a writing task of writing a diverse paragraph as an online stimulation task. The stimulation block will be preceded and followed by a writing assessment and TMS acute side effects survey to assess safety of the stimulation. Visit 3, 4, and 5 will occur 1 week apart. Subject will undergo fMRI after each of the 3 TMS visits.

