 5. Of note, although both writing task and writing assessment will comprise of a writing and non-writing sample on a digital tablet, writing assessment will additionally entail video recording of the subjects' writing from the neck down, focused on subjects' arms and hands. These recordings will be used to complete Writer's Cramp Rating Scale (WCRS)(46) and Adult dystonia and disability rating scale (ADDS)(45) by an observer blinded to treatment. Overall, writing task is different from writing assessment in that writing task will only be used as part of the investigational treatment while writing assessment will consist of outcomes measures data collected for analysis.
 6. Data from visits 3, 4 and 5 will be used to determine safety of TMS stimulation protocol and feasibility of writing task and fMRI with stimulation protocol.

Selection of Subjects

- List inclusion/exclusion criteria and how subjects will be identified.

Inclusion criteria:

Healthy Control Participants:

1. 18yrs and older
2. **Left or Right hand dominance**
3. Age-matched to Focal Hand dystonia patients
4. Must be able to sign informed consent

5. Must be literate

Focal Hand dystonia Patients:

1. 18yrs and older
2. **Left or Right hand dominance**
3. **Diagnosed with Writer's Cramp dystonia in left or right hand**
4. Must be able to sign informed consent
5. Must be literate

Exclusion criteria:

Healthy Control Participants and Focal Hand dystonia Patients (visit 1)

1. Other neurological movement disorders diagnoses including other types of dystonia, Parkinsonism, or essential tremor
2. Botulinum toxin injections within 3months of research study
3. Medications with effects on the central nervous system including anticholinergic, benzodiazepines, and muscle relaxants among others within 1 week of the study
4. No physical or occupational therapy of the upper extremities

Healthy Control Participants (visits 2-5) and Focal Hand dystonia Patients (visits 2-5):

1. Other neurological movement disorders diagnoses including other types of dystonia, Parkinsonism, or essential tremor
2. Botulinum toxin injections within 3months of research study
3. Medications with effects on the central nervous system including anticholinergic, benzodiazepines, and muscle relaxants among others within 1 week of the study
4. No physical or occupational therapy of the upper extremities
5. Any contraindications to MRI (ie: metal in body or implanted medical devices, etc)

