The most commonly reported side effect of rTMS is headache. This headache is typically of a muscle-tension type. It usually develops during or immediately after the stimulation and may last for minutes to hours following the end of the stimulation. It is typically limited to the day of stimulation, and usually responds promptly to single doses of over the counter pain medications. Neck pain or scalp pain may also occur. Both are usually managed easily with over-the-counter analgesics. Participants may take Advil or Tylenol to reduce discomfort. Tylenol or Advil will be used according to recommended dosage, ensuring that the participant has no allergies and has not taken other NSAIDS or acetaminophen. Liver damage can occur when more than 4,000 mg of acetaminophen are taken in 24 hours or when taken with alcohol. Ibuprofen can cause stomach bleeding in certain individuals or when not adhering to dosage recommendations. Once the Advil or Tylenol has had time to take effect, we will resume stimulation. If there is still discomfort, topical lidocaine cream may be applied to the area of the scalp where stimulation occurs. Topical lidocaine has been shown to relieve discomfort resulting from rTMS for some people. Topical lidocaine should not be used on large areas or on cut, irritated or swollen skin. Twenty minutes must be allowed for the lidocaine cream to take effect. If implemented, Tylenol, Advil, and lidocaine cream will be used as directed.

As noted in Rossi et al(47), Loo and colleagues reported mild and transient changes in auditory threshold in two depressed patients following a 2-4 week rTMS course of rTMS. Cases of tinnitus have been reported after rTMS treatments. In addition, recently in a study investigating the effects of rTMS on symptoms of depression, a patient experienced moderate to severe tinnitus after an rTMS session in which earplugs were not used. Rossi et al. recommended that hearing protection always should be worn during rTMS application, and that individuals with cochlear implants not receive rTMS. In the current study, earplugs will be worn by all subjects during rTMS procedures. Individuals with cochlear implants will be excluded from participation.

Illicit drugs such as cocaine can reduce the seizure threshold. As a result, all subjects will undergo urine toxicology test prior to each TMS session and positive subjects will be excluded from the study. Risks to the unborn children of

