Our preliminary analysis of the Duke patient population reveals sufficient population of FHD subjects to recruit for our study at Duke University. Our electronic patient database identifies 186 Duke patients with a specific diagnosis of organic writer's cramp (ICD 9 code 333.84). Because ICD 10 code does not have a specific writer's cramp diagnosis, we suspect that more cases are included within the ICD G24.9 (focal dystonia) group. Therefore, the primary care providers for all 837 subjects with either of these codes may be contacted by research coordinator for patient candidacy for this research study as detailed in Section 6 eIRB submission form.

Analysis and Statistics: [name] in the Department of Neurology, **[name] and [name] in the BERD core of the Statistics Department** will be **involved** the de-identified data **analysis** but will be not involved in collecting the data. Visit 1 data of handwriting metric differences between healthy participants and focal hand dystonia patients will establish writing metric sensitivity at our site and recalculate power analysis to adjust cohort sizes, or improve technique, as indicated for visits 2, 3, and 4. For Visit **3 -5**, a two-way ANOVA will be performed with groups (healthy vs dystonia) and stimulation type (task during vs after stimulation) as the main factor within subjects. A two-way repeated measures ANOVA will be conducted with stimulation type (task during vs after stimulation) and treatment type (sham vs active) as the main factors between subjects for each handwriting measure.

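### Patients can be excluded after one or two of the three TMS sessions, and a classical repeated-measures ANOVA would drop many of them; a mixed model on all completed sessions would keep their data

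*Combined protocol and SAP*

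**What the plan says.** **Sessions.** Each of the 20 dystonia patients has three TMS visits: "2 visits will involve active TMS and 1 visit will be sham TMS" (Purpose of the Study). The active visits are one to premotor cortex and one to primary sensory cortex. On spacing, "Visit 3, 4, and 5 will occur 1 week apart" (Design & Procedures, step 4). The end of Background & Significance says that the two active visits serve to find the better of the two targets.

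**Exclusion.** The TMS Adverse Events Plan states that "all subjects will undergo urine toxicology test prior to each TMS session and positive subjects will be excluded from the study". The same section has female subjects take a pregnancy test before every MRI and TMS session, and excludes those who are pregnant. The shorter wording in Purpose of the Study and in Design & Procedures is "A urine drug screen and pregnancy test prior to visits 3-5", with no consequence given.

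**Analysis.** Under Analysis and Statistics, "A two-way repeated measures ANOVA will be conducted with stimulation type" (writing during or after stimulation) and treatment type (two levels, sham and active) as factors, for each handwriting measure.

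**Feasibility.** Step 6 of Design & Procedures says that data from visits 3 to 5 will serve to judge safety and "feasibility of writing task and fMRI with stimulation protocol". No criterion or denominator follows.

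**What is absent.** The prompt at the head of Data Analysis & Statistical Considerations asks how ineligible subjects are handled and who is analysed. The text beneath it names no analysis set, missing-session method or replacement rule, and does not say whether data collected before an exclusion are kept. Its only allowance for loss is a 31% screening failure rate.

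**The concern.** Testing is repeated before each weekly session and a positive result ends participation. A patient can therefore have one or two good sessions and no more. In its classical form, a repeated-measures ANOVA needs every within-patient cell filled and deletes the whole patient otherwise. With 20 patients, each one deleted is 5% of the sample.

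Two things are at stake. The first is some precision in the active-versus-sham contrast, because usable sessions are thrown away. The second is that the choice is left open: whoever runs the analysis can decide how to treat these patients after seeing who left and what their data look like. Item 6 under Data Storage and Management asks for the statistical approach to be settled beforehand and stated clearly. The missing feasibility denominator is a related but lesser gap.

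**Working it through.** The plan has no figure of its own on loss between visits 3 and 5, so there is none to reproduce. The loss rates below are assumptions.

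**Inputs from the plan:** 20 patients; 3 sessions (2 active, 1 sham); a test before each; exclusion after a positive result.

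**Assumptions:** the same loss probability p at each of the three tests, independent between patients; permanent exclusion; session order balanced; correlation 0.3 to 0.6 between a patient's sessions.

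**Step 1: who is left.** Of 20 patients reaching the Visit 3 test:

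- no session: 20p
- one session only: 20(1-p)p
- two sessions only: 20(1-p)²p
- all three: 20(1-p)³

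| p | none | one | two | all three |
|---|---|---|---|---|
| 5% | 1.0 | 0.95 | 0.90 | 17.1 |
| 10% | 2.0 | 1.80 | 1.62 | 14.6 |
| 15% | 3.0 | 2.55 | 2.17 | 12.3 |

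The partly treated are the middle two columns: about 1.9, 3.4 and 4.7 patients. A patient positive before Visit 3 has had no TMS, and no model can use sessions that never took place. At p = 1% or 2%, completers are 19.4 or 18.8.

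**Step 2: whom the ANOVA drops.** This depends on how it is run.

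- *Sham versus active, as written.* Sham plus one active session can fill the treatment cells. With balanced order, a two-session patient has had sham with probability 2/3. Evaluable patients are 20(1-p)³ + (2/3) × 20(1-p)²p:
  - 5%: 17.15 + 0.60 = 17.8
  - 10%: 14.58 + 1.08 = 15.7
  - 15%: 12.28 + 1.45 = 13.7
- *Premotor, sensory and sham compared*, which the target question calls for. Only the 17.1, 14.6 or 12.3 three-session patients remain.

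**Step 3: cost in precision for mean active minus sham.** Let σ² be the variance of one session's measure and ρ the correlation between sessions. With n complete patients and contrast weights ½, ½, -1, the variance is 1.5σ²(1-ρ)/n. Relative to 20 complete patients, the complete-case standard error grows by √(20/n):

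- 5%: √(20/17.15) = 1.08
- 10%: √(20/14.58) = 1.17
- 15%: √(20/12.28) = 1.28

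Much of that growth comes from sessions that never happened. The part that the analysis choice controls is the ratio of the complete-case standard error to that from generalised least squares on all available sessions:

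| p | permanent exclusion | a missed session, then return |
|---|---|---|
| 5% | about 1.02 | about 1.05 |
| 10% | 1.04-1.05 | about 1.10 |
| 15% | 1.07-1.08 | about 1.16 |

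The middle column matches the exclusion rule as worded. Its lower end at 15% falls to about 1.06 in a large-sample calculation, so the last digit is not firm. At 1-2% per session the ratio is 1.01 or less.

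**Step 4: feasibility.** The expected share completing all three sessions, (1-p)³ of those who start Visit 3, is 86%, 73% and 61%. Of those who receive a first session it is (1-p)², or 90%, 81% and 72%. The figure moves with the denominator, and the plan names none.

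**The case against.** Several objections are sound and set the limits of this point.

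- **A reader might infer that the ANOVA needs all three sessions and that a partly treated patient contributes nothing.** The documents do not say so. The treatment factor has two levels, so sham plus one active session could still count. The separate healthy-versus-dystonia ANOVA has no sham factor, and safety data count in any case. No complete-case rule is written. It is the usual behaviour of the classical method, not a stated choice.
- **A reader might infer that feasibility is overstated by construction.** That would need a denominator of completers only, which appears nowhere. Exclusion from the study may simply mean no further stimulation. The result is undetermined, not biased.
- **A reader might add other exit routes.** The consent text, "Subjects can opt in or out of visits 2, and 3-5 of the research study", treats visits 3 to 5 as one block and does not describe leaving between sessions. The discomfort text concerns relief and resuming stimulation. Neither is a stated mid-sequence exit rule.
- **The gain is small.** With permanent exclusion it is about half of what independent missed sessions would suggest, and negligible if positive tests are rare. For a self-described pilot, simply stating the analysis set and missing-session rule would close most of the gap.

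What remains is that mid-sequence exclusion is explicit, the named method in its classical form deletes patients with empty cells, and the plan says nothing to prevent it. A model that avoids the deletion costs little more than a sentence stating the rule.

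**Conclusion.** The point holds as a cheap improvement, not as a flaw that undermines the study. The plan allows exclusion after one or two sessions and names an analysis that, run classically, discards any patient with an empty cell. It gives no rule for these patients. At an assumed 5%, 10% or 15% permanent loss per session, completers fall to 17.1, 14.6 and 12.3 of 20. The avoidable part of the precision loss is about 2%, 4-5% and 7-8% in the standard error of mean active minus sham. These sizes rest on assumed loss rates, balanced order and correlation of 0.3 to 0.6, none of which the documents give. The documents do not support saying that every partly treated patient is lost, or that the feasibility result is inflated. The feasibility denominator is missing detail and secondary.

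**What to change.** **Main change (Analysis and Statistics).** Replace the two-way repeated-measures ANOVA for visits 3 to 5 with a linear mixed model: a patient random effect, with session condition (premotor, primary sensory, sham) and task timing as within-patient fixed effects. Fit it to all completed sessions of every patient with at least one TMS session. State that data collected before an exclusion are kept. Sham versus active and the comparison of targets are then contrasts from one model.

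**Secondary reporting.** Give feasibility as patients completing all three sessions with usable writing and fMRI data, divided by all who start Visit 3 (defined as reaching the pre-session test). Add an exact 95% confidence interval and the reasons for non-completion by visit.

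**Reconcile wording.** Purpose of the Study, Design & Procedures and the TMS Adverse Events Plan should agree on the timing and consequence of the drug screen. The rule on who may be stimulated is not part of this change.

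**Cost.** Plan wording and a standard model, with no extra patients or visits. The model assumes that sessions are missing at random, which cannot be verified with 20 patients and should be stated. The feasibility figure may look less favourable than one based on completers.

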Visit 1: 70 HV and 70 FHD subjects will be recruited at the Duke BSRC in the Duke Main Hospital. After the study team consents the subject, the following will be obtained: Patient's medical history to evaluate appropriateness of dystonia diagnosis. Patient will also be asked about the symptoms and signs of dystonia on rating scales including Adult dystonia and disability rating scale (ADDS)(45) Burke Fahn Marsden Rating Scale (BFM) and Pain Scale.

Subjects will then be asked to perform 3 writing samples (WT-1, WT-2, and WT-3) and non-writing samples on a digital tablet. WT-1 will be a single sentence written repeatedly 10 times to quantify writing performance. WT-2 will be a different single sentence written 10 times. WT-3 will be a linguistically diverse paragraph. All writing tasks will be performed by subjects using their dominant **left or right hand**. All subjects will be videotaped from the neck down, focused on their arms and hands during the writing sampling to allow careful examination of subject's hand and finger movements for Writer's Cramp Rating Scale (WCRS)(46) by 2 expert physicians (one Duke physician and one external physician) blinded to the group identity.

The patients videos of writing assessments are reviewed by the research team to ensure no personal identifier information (face, name, DOB) is visible. Videos are then deidentified and an ID number is assigned to each video for blinding purposes. The research staff then imports the videos to a secure Duke server including DukeBox and Duke PACE environment. The external physician will only access the videos using the Duke PACE environment while the internal Duke physician may access the videos using either the Duke Neurology server, DukeBox or Duke PACE environment. The physicians will rate the participants' writing assessments using established dystonia rating scales (WCRS, BFM).

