The study team will email the research flyer and research study brochure to these locations so that they can be posted or distributed and also email Dystonia research foundations and Dystonia support groups in neighboring states. The study team will also give engage Dystonia support groups in nearby states and provide information about the study using an IRB-approved presentation. The powerpoint presentation submitted with this IRB application is the presentation I would give to patients in the Dystonia support groups to help with raising awareness about the study. I have added language that is highlighted on page 8 of the IRB protocol to describe this additional recruitment material. The study team will also post the study flier information on the DukeList website under volunteers to recruit healthy volunteers for the study. We will have a waiver in place to handle any self-referral calls or emails.

All potential subjects with writer's cramp or healthy volunteers will be introduced to the study through the contact approaches listed above and if agreeable, will have an in-person screening by the study team during visit 1 at Duke Brain Stimulation Center at Duke Main hospital.

The study team will also review the clinic schedule in the Duke Movement Disorders Center for potential FHD subjects seen by Movement Disorders Specialist who meet the basic inclusion/exclusion criteria and have appointments that day. While recruiting FHD potential subjects, we may also introduce the study to caregivers who accompany the patient to the clinic and ask if they would also like to be part of the study and possibly enroll as a Healthy Control subject.

To recruit healthy subjects, BIAC's healthy volunteer registry will be also used and guidelines followed as indicated in their IRB Pro 00010672. We will also recruit healthy participants from Duke Clinical Research Unit Volunteer Registry and follow guidelines from their IRB Pro 00010672.

Subjects will be reimbursed \$50 for each of the five visits. Subjects completing all 5 visits will receive a maximum of \$250.

Consent Process

- Complete the consent section in the iRIS Submission Form.

Subject's Capacity to Give Legally Effective Consent

- If subjects who do not have the capacity to give legally effective consent are included, describe how diminished capacity will be assessed. Will a periodic reassessment occur? If so, when? Will the subject be consented if the decisional capacity improves?

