Writer's cramp behavioral data: Endpoints: Objective handwriting parameters of duration of writing, speed of handwriting, fluency of writing movements, axial pen pressure and interpretability of handwriting will be collected using a digital tablet and a pressure sensitive pen for data analysis. Additionally, an observer blinded to subject group will complete Writer's cramp rating scale(46) and BFM Rating Scale from video recordings of subjects performing each writing task (WT-1, WT-2 and WT-3). At the initial visit, patient's medical history will be collected to evaluate appropriateness of dystonia diagnosis. Patient will also be asked about the symptoms and signs of dystonia on rating scales including Adult dystonia and disability rating scale (ADDSD)(45) Burke Fahn Marsden Rating Scale (BFM) and Pain Scale to compare their baseline symptoms before and after all 4 visits.

Sample Size justification: A review of prior research studies employing TMS in writer's cramp and healthy volunteers measuring handwriting showed statistically significant effect sizes of 15-20% on various measures of writing performance using 6-12 subjects per group(38-40,43). A power analysis of our preliminary writing behavior data from 30 subjects in visit 1 demonstrated sample size of 60 in TMS for effect size of 30% with $\alpha = 0.05$. Assuming that I will be able to achieve similar sensitivity in writing metrics, I propose to study 20 patients in TMS group using writing task and fMRI as outcome measures for analysis (visit 1). Due to the pilot nature of fMRI and TMS stimulation parameters, the minimum number of subjects needed to calculate statistical power were selected. Therefore, in order to reach pilot data set of 20 patients in TMS group with 31% screening failure rate, we need approximately 70 FHD subjects. The 70 healthy volunteers will allow us to do a better statistical power analysis of clinical and fMRI outcomes measures to evaluate effect size for TMS As a result, we would like to increase our overall goal enrollment target to 140

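### For the 20 patients who receive TMS, the stated before-after comparison of ADDS, BFM and Pain pools active and sham sessions, and no active-versus-sham analysis of these scales is planned

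*Combined protocol and SAP*

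**What the plan says.** Under Data Analysis & Statistical Considerations (Writer's cramp behavioral data: Endpoints), patients are asked at the initial visit about their symptoms on the ADDS and two further scales: "Burke Fahn Marsden Rating Scale (BFM) and Pain Scale to compare their baseline symptoms before and after all 4 visits". This is the only comparison stated for the patient-asked scales.

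The treatment structure is in Purpose of the Study and in Design & Procedures (Visits 3, 4 and 5, step 4). The number treated is given as "20 focal hand dystonia subjects who completed visits 1 and 2 will also be recruited to undergo 3 visits of TMS stimulation". For each of them, "2 visits will include active TMS stimulation while the remaining one visit will be a control sham stimulation"; one active session is premotor and the other primary sensory. On spacing, "Visit 3, 4, and 5 will occur 1 week apart".

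Three other places bear on the point:

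- **Design & Procedures, Visits 3, 4 and 5, steps 4 and 5.** A writing assessment comes before and after each stimulation block, active or sham. It is video-recorded, and an observer blinded to treatment completes the WCRS and the ADDS from the recordings. The Pain Scale does not appear in these steps.
- **Design & Procedures, Visit 1.** Two physicians rate the writing-assessment videos with the WCRS and the BFM.
- **Analysis and Statistics.** The repeated measures ANOVA that contrasts sham with active is specified for the handwriting measures and for nothing else.

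On the number of visits, Subject Recruitment and Compensation says: "Subjects will be reimbursed \$50 for each of the five visits".

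**The concern.** Purpose of the Study asks whether stimulation can give lasting improvement in dystonic symptoms. ADDS, BFM and Pain bear directly on that question. A change from Visit 1 to the end of the study mixes any active effect with response to the procedure, expectation, regression to the mean and drift over time. An improvement could be read as benefit when none of it came from active stimulation, and a flat result could hide a real effect. The trial already runs a sham session in each TMS patient, but the stated comparison does not use it. Nor do the other 50 dystonia subjects (70 − 20) supply a control for time, because no repeat of these scales is described for them.

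**Working it through.** The plan gives no figure that depends on this point, so there is nothing to reproduce. The check is whether active minus sham can be estimated under each reading of the endpoint sentence.

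**Inputs.** 20 TMS patients; per patient one premotor, one primary sensory and one sham session (Purpose of the Study; Design & Procedures, step 4); α = 0.05 (Sample Size justification). The plan does not state sidedness; two-sided is assumed here.

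**Start-to-end reading.** Let m and s be the premotor and primary sensory effects that persist to the end, H the total non-specific response to the three sessions, and τ the change with time since Visit 1. Each patient supplies one number:

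D = m + s + H + τ

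The design row is (1, 1, 1, 1), which has rank 1 for four unknowns. The average active effect, with weights (½, ½, 0, 0), is not a multiple of that row, so it is not estimable at any sample size.

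**Session-level reading.** With a change from before to after each block, and h the non-specific response within a session:

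- premotor session: m + h
- primary sensory session: s + h
- sham session: h

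This has rank 3 for three unknowns. Premotor minus sham gives m, and primary sensory minus sham gives s, provided there is no carryover or period effect.

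**What an uncontrolled test could show.** Suppose there is no true active effect and the non-specific change is δ, in SDs of the within-patient change. The δ values are assumptions, since the documents give no SD for these scales. For a paired t-test with n = 20, the noncentrality is δ√20, on 19 degrees of freedom:

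| δ (assumed) | δ√20 | Probability of p < 0.05 |
|---|---|---|
| 0.2 | 0.89 | about 14% |
| 0.5 | 2.24 | about 57% |
| 0.8 | 3.58 | about 92% |

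**What the session-level contrast could detect.** By the same calculation, 20 paired differences give 80% power at a standardized within-patient difference of about 0.66, and 90% at about 0.76. This is one contrast at α = 0.05, with no adjustment for several scales or two sites.

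**Status of each scale at the TMS visits.**

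| Scale | Measured around each block? | Active-versus-sham analysis specified? |
|---|---|---|
| ADDS | Yes, from video, blinded to treatment | No |
| BFM | Probably; video rating is described under Visit 1 | No |
| Pain | Not scheduled | No |

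On the start-to-end reading, the final Pain value has no scheduled time either.

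**Visit count.** The endpoint sentence counts four visits; the compensation text and the design describe five. Analysis and Statistics also mixes the two, naming visits 2, 3 and 4 as those to be adjusted after Visit 1 and then visits 3 to 5 for the ANOVA.

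**The case against.** The strongest reply is that much of the needed measurement is already in the protocol. ADDS is rated by a treatment-blinded observer before and after every block, active and sham. The term writing assessment is used both for the videos that the physicians rate with the BFM and for the recordings at visits 3 to 5, so BFM ratings by session are likely too. A reader might infer from the endpoint sentence that there will be no sham-controlled information on any of these scales. For ADDS the documents contradict that, and for BFM it is doubtful. This part of the objection stands. What it leaves open is the analysis, which is specified for none of the three scales, and the Pain Scale, which is not scheduled.

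Second, the sentence could mean before and after each visit. On that reading the contrast is estimable. But the sentence opens at the initial visit and speaks of baseline symptoms, so start-to-end is the more natural sense. Even on the other reading, the visit procedures do not schedule Pain and no active-versus-sham analysis follows.

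Third, these scales are not central. Design & Procedures, step 6, assigns the data from visits 3 to 5 to safety and feasibility; the sample size text names the writing task and fMRI as outcomes; and the WCRS is already rated blind around each block. This also stands, and it limits how much the point matters.

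**Conclusion.** The point holds in a limited form. For the 20 TMS patients, not all 70 dystonia subjects, the only stated comparison of the patient-asked ADDS, BFM and Pain Scale cannot isolate active stimulation on its natural reading. On either reading, no active-versus-sham analysis of these scales is specified. The gap is complete for Pain, one of analysis for ADDS, and probably one of analysis only for BFM.

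Two stronger inferences are not supported. Giving every TMS patient both active and sham is the ordinary crossover structure and is not a fault; the fault lies in when the scales are scored and how they are compared. Nor do the documents show a decision to discard the sham control: the sentence is ambiguous and its visit count does not match the design.

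The estimability result needs no numerical assumption. The 14%, 57% and 92% depend on the assumed size of the non-specific change and are illustrative. In a 20-patient pilot where these scales are secondary, the point justifies an amendment but does not threaten the trial as a whole.

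**What to change.** 1. Score the Pain Scale and BFM at the same fixed points in each of visits 3, 4 and 5, alongside the writing assessments and ADDS ratings already planned. State whether each score is patient-asked or rated from video.
2. Extend the active-versus-sham analysis to ADDS, BFM and Pain. The analysed quantity should be the within-patient change over the session for each active site minus the change for sham. The ANOVA as written has a single sham-versus-active factor, described as between subjects, so the extension should state that the comparison is within patients and keep the two sites apart.
3. Label the change from Visit 1 to the end of the study as descriptive only.
4. Reconcile the four-visit and five-visit counts.

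The cost is a wording amendment and a few minutes of extra questions at visits that already take place.

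Two limits remain. Sessions are one week apart, while Background & Significance cites an earlier study with a two-week benefit, so an active effect may carry into the next session. The documents also do not describe a randomized or balanced session order, so order effects may not cancel. Both should be acknowledged when the contrast is reported.
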